### Study Discontinuation

Calculating the percentages based on the number of subjects enrolled, summarize the following:

- The number and percentage of subjects who completed the study,
- The number and percentage of subjects who discontinued the study
- The number and percentage of subjects who discontinued the study by reason

#### **6.2.2 Protocol Deviations**

Protocol deviations will be documented and explained by the investigator and classified as major or minor by the clinical monitor.

The number and percentage of subjects with at least one major protocol deviation will be summarized for each protocol deviation category based on the safety population.

All protocol deviations will be listed.

#### **6.2.3 Background and Demographic Characteristics**

Demographic information including age at first dose in years, sex, ethnicity, race, height in meters, weight in kilograms, body mass index in  $\text{kg}/\text{m}^2$ , and ECOG performance status will be tabulated for the safety population. Descriptive statistics, including number of patients, mean, standard deviation, median, minimum, and maximum for continuous parameters, as well as percentages for categorical parameters, will be presented.

Age in years at the date of first dose will be computed as an integer using the date of birth and the date of first dose.

Body mass index will be computed as (weight in kilograms / (height in meters)).

Tobacco use history (never, current, previous) and for those with current or previous tobacco use the number of years a subject is/was a smoker and the average number of cigarettes, cigars, pipes, and pack of chewing tobacco per week, will be summarized descriptively for the safety population.

Non-metastatic lung cancer history will be summarized for the safety population by presenting summary statistics for histology (squamous, non-squamous, and type of non-squamous), initial diagnosis staging (Stages IB, II, IIIA, and selected IIIB), and time from initial diagnosis to first dose. Time from initial diagnosis to first dose is computed as the date of first dose in Cycle 1 minus the date of initial diagnosis, plus one day.

Lung cancer molecular profile will be summarized for the safety population by presenting descriptive statistics for derived Epidermal Growth Factor Receptor (EGFR) mutation (positive, negative/unknown), derived anaplastic lymphoma kinase (ALK) rearrangement detection status (yes, no/ unknown), and number and percentage for each binary group category and combined mutually exclusive group category of PD-L1 IHC status by SP142 method. This lung cancer molecular profile will be used in efficacy analyses.

PD-L1 status of patients using SP142 method can be derived as such: group the Tumor Cell (TC) score and Immune Cell (IC) score (both range from 0 – 100) into the following groups:

- Total Perc Cells Membrane Stain: TC0 [0,1), TC1 [1,5), TC2 [5,50), TC3 [50-100]
- Perc Positive Infiltrate In Tumor Mass: IC0 [0,1), IC1 [1,5), IC2 [5,10), IC3 [10,100]

Derive the binary grouping scores: TC3/IC3 (categorized as TC3IC3, TC012IC012, unknown), TC2/IC2 (categorized as TC23IC23, TC01IC01, unknown) and TC1/IC1 (categorized as TC123IC123, TC0IC0, unknown) and the combined mutually exclusive grouping score: TCIC4GRP (categorized as TC3 or IC3, TC0 or IC0, TC2/3 or IC2/3, TC1/2/3 or IC1/2/3, unknown).

For derived EGFR status and derived ALK status, local lab (CRF) value will be used first; if there is missing data in local lab value, central lab value at screening will be used second, and finally if there is missing data in central lab value at screening, central lab value at surgery will be used.

Local lung cancer molecular profile per CRF will be summarized for the safety population by presenting descriptive statistics for Epidermal Growth Factor Receptor (EGFR) mutation (positive, negative, and unknown), anaplastic lymphoma kinase (ALK) rearrangement detection status (yes, no, unknown), and PD-L1 IHC status (negative, positive, unknown).

Results of the ventilation/perfusion scan performed at screening will be summarized for the safety population by presenting summary statistics for scan performed (yes, no) and specific results (no perfusion deficit, perfusion deficit with matched ventilation deficit, ventilation perfusion mismatch, perfusion deficit that corresponds to parenchymal abnormality on chest x-ray, multiple segmental perfusion deficits with normal ventilation).

#### **6.2.4 Treatment Exposure and Compliance**

##### Neoadjuvant Atezolizumab Therapy Phase

Treatment exposure and compliance will be examined in the Neoadjuvant Atezolizumab Therapy Phase of the study by summarizing overall the number of cycles initiated, infusion cycle intervention status (yes, no), and reason for infusion intervention (infusion related reaction [IRR], adverse event not considered IRR, other) for the safety population.

##### Surveillance/Survival Follow-up Phase

---

The same treatment exposure and compliance will also be summarized for the Surveillance/Survival Follow-up Phase.

#### **6.2.5 Prior and Concomitant Medications and Therapies**

All reported medications and therapies, whether determined to be prior or concomitant uses, will be coded using the Genentech, Inc. Drug Thesaurus. Levels of summarization will include drug class and standardized term.

Concomitant medications are defined as non-study medications with a stop date on or after the first dose of study drug, and a start date on or before the date of the subject's last visit in the study. Medications that started prior to the first dose of study drug and are ongoing will be classified as concomitant. Medications that have a stop date prior to the first dose of study drug will be flagged as 'prior'.

At each level of summarization (drug class and standardized term), a subject will be counted only once for each medication he/she has within that level. Prior and concomitant medications will be summarized in separate tables for each study phase separately. The percentage of safety population subjects having had at least one prior or concomitant medication at each level will be calculated.

Data listings will be provided for all prior and concomitant medications.

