Approximately 180 patients with histologically documented Stage IB, II, IIIA, and selected IIIB NSCLC and are eligible for surgical resection with curative intent will be enrolled in the Neoadjuvant Atezolizumab Therapy Phase of this study. Approximately 50 patients who complete neoadjuvant atezolizumab therapy are expected to continue on to the Adjuvant Atezolizumab Therapy Phase.

4.1.1 **Inclusion Criteria**

Neoadjuvant Atezolizumab Therapy

Patients must meet the following criteria for study entry:

- Signed Informed Consent Form
- Age \geq 18 years
- Able to comply with the study protocol, in the investigator's judgment
- Pathologically documented NSCLC
 - Stage IB, II, IIIA, or selected IIIB, including T3N2 or T4 (by size criteria, not by mediastinal invasion) NSCLC (based on the 8th edition of the American Joint Committee on Cancer [AJCC] Non-Small Cell Lung Cancer Staging system; see [Appendix 4](#)). Note: Patients may be enrolled based on clinical stage, but documentation of nodal involvement by endobronchial ultrasound (EBUS) or mediastinoscopy for patients with clinical Stage II and IIIA disease is encouraged.
- Measurable disease, as defined by RECIST v1.1
- NSCLC must have a solid or subsolid appearance on CT scan and cannot have a purely ground glass opacity (GGO) appearance. For subsolid lesions, the tumor size (i.e., clinical T stage) should be measured based on the solid component only, exclusive of the GGO component
- Evaluated by the operating attending surgeon prior to study enrollment to verify that the primary tumor and any involved lymph nodes are technically completely resectable
- Adequate pulmonary function to be eligible for surgical resection with curative intent
 - Pulmonary function tests (PFTs) must have been performed within 6 months of planned resection and repeated at screening and should include lung volumes, spirometry, and a diffusion capacity. Abnormal PFTs may be further evaluated with quantitative ventilation/perfusion scanning or cardiopulmonary exercise testing. Postoperative percent predicted forced expiratory volume in 1 second (FEV1) and diffusion capacity must be $\geq 40\%$ and/or maximal oxygen consumption (VO_2 max) should be > 10 mL/kg/min.

- Adequate cardiac function to be eligible for surgical resection with curative intent
 - If clinically indicated, patients with underlying ischemic or valvular heart disease should be evaluated preoperatively by a cardiologist.

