4.4 CONCOMITANT THERAPY

Concomitant therapy includes any medication (e.g., prescription drugs, over-the-counter drugs, vaccines, herbal or homeopathic remedies, nutritional supplements) used by a patient from 7 days prior to initiation of atezolizumab until the following visit: 1) For patients who will receive adjuvant atezolizumab treatment – until the adjuvant atezolizumab completion/ discontinuation visit, or 2) For patients who will not receive adjuvant atezolizumab treatment – until the Post-surgery Visit. All such medications should be reported to the investigator and recorded on the Concomitant Medications eCRF.

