## 5. ANALYSIS POPULATIONS

Data will be summarized using the following analysis populations.

- All Enrolled Subjects: This analysis population will include all enrolled subjects, regardless of whether they received any amount of study drug. The all enrolled subjects population will be used for the summarization of subject disposition.
- Safety Population: This analysis population will include all enrolled subjects who have received any dose of study drug. The safety population will be used for the analysis of safety measures.
- Efficacy Population: This analysis population will include all enrolled patients who have received at least one dose of the study drug and who do not have EGFR or ALK mutant tumors.
- Primary Efficacy Population: This analysis population will include all efficacy population subjects, excluding patients who have not received surgery after neoadjuvant treatment with Atezolizumab, and excluding subjects who have not had a complete resection. This population will be used for primary efficacy analysis. For the primary efficacy population, if major pathological response is unable to be assessed, then it will remain undetermined and the subject will be removed from this population.

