	Table 14.1.10.2	Study Drug Exposure, Surveillance/Survival Follow-up Phase	Safety Population
S, P	Table 14.1.11.1	Prior Medications	Safety Population
S, P	Table 14.1.11.2	Concomitant Medications, Neoadjuvant Atezolizumab Therapy Phase	Safety Population
	Table 14.1.11.3	Concomitant Medications, Surveillance/Survival Follow-up Phase	Safety Population
E, P	Table 14.2.1	Primary Efficacy Analysis for Major Pathologic Response Rate	Primary Efficacy Population
E, P	Table 14.2.2.1	Major Pathologic Response Rate within PD-L1 Group	Efficacy Population
E, P	Table 14.2.2.2	Investigator-assessed Response Rate within PD-L1 Group	Efficacy Population
E, P	Table 14.2.3.1	Survival Analysis for Overall Survival (OS)	Efficacy Population

Interim Analysis Flag	Output Type and Number	Output Title	Output Population
E, P	Table 14.2.3.2	Survival Analysis for Disease-Free Survival (DFS)	Primary Efficacy Population
E, P	Table 14.2.3.3	Survival Analysis for Event-Free Survival (EFS)	Efficacy Population
E, P	Table 14.2.3.4	Survival Analysis for Overall Survival (OS)	Efficacy Population
E, P	Table 14.2.3.5	Survival Analysis for Disease-Free Survival (DFS) by Major Pathologic Responder (MPR)	Primary Efficacy Population
E, P	Table 14.2.3.6	Survival Analysis for Event-Free Survival (EFS) by Major Pathologic Responder (MPR)	Efficacy Population
E, P	Table 14.2.3.7	Survival Analysis for Overall Survival (OS) by PD-L1 Group	Efficacy Population
E, P	Table 14.2.3.8	Survival Analysis for Disease-Free Survival (DFS) by PD-L1 Group	Primary Efficacy Population
E, P	Table 14.2.3.9	Survival Analysis for Event-Free Survival (EFS) by PD-L1 Group	Efficacy Population
S, E, P	Table 14.3.1.1.1	Overview of Adverse Events by Highest NCI CTCAE Grade, Neoadjuvant Atezolizumab Therapy Phase	Safety Population
	Table 14.3.1.1.2	Overview of Adverse Events by Highest NCI CTCAE Grade, Surveillance/Survival Follow-up Phase	Safety Population
S, E, P	Table 14.3.1.2.1	Adverse Events by Highest NCI CTCAE Grade, Neoadjuvant Atezolizumab Therapy Phase	Safety Population
	Table 14.3.1.2.2	Adverse Events by Highest NCI CTCAE Grade, Surveillance/Survival Follow-up Phase	Safety Population
S, E, P	Table 14.3.1.2a	Adverse Events by Highest NCI CTCAE Grade, Both Study Phases	Safety Population
S, E, P	Table 14.3.1.2b	Adverse Events With Onset Prior to Date of Surgery by Highest NCI CTCAE Grade, Neoadjuvant Atezolizumab Therapy Phase	Safety Population

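### Table 14.1.11.3 divides later-phase medication use by the whole safety population, although collection ends at the Post-surgery Visit unless the patient receives adjuvant atezolizumab

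*SAP*

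**What the plan says.** SAP 6.2.5 asks for medication summaries by phase: "Prior and concomitant medications will be summarized in separate tables for each study phase separately". SAP Table 3 lists one concomitant-medication table for the neoadjuvant phase (14.1.11.2) and one headed "Concomitant Medications, Surveillance/Survival Follow-up Phase" (14.1.11.3). Both carry the safety population as output population. SAP 3.1 places adjuvant atezolizumab in the later of these two phases.

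The definition rests on dates alone. It opens "Concomitant medications are defined as non-study medications with a stop date on or after the first dose of study drug, and a start date" and closes with the upper limit, "a start date on or before the date of the subject's last visit in the study". Neither limit is a phase boundary.

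The denominator is stated in the same section: "The percentage of safety population subjects having had at least one prior or concomitant medication at each level will be calculated". SAP 5 defines the safety population: "This analysis population will include all enrolled subjects who have received any dose of study drug".

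Collection is narrower than that. Protocol 4.4 sets two end points. With adjuvant atezolizumab, medications are recorded until its completion or discontinuation visit. The second rule begins "For patients who will not receive adjuvant atezolizumab treatment" and ends collection at the Post-surgery Visit. Footnote qq repeats both rules in protocol Appendix 1 and in the SAP 4 schedule. On numbers, protocol 4.1 plans about 180 patients and says that approximately "50 patients who complete neoadjuvant atezolizumab therapy are expected to continue on to the Adjuvant Atezolizumab Therapy Phase".

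**The concern.** A percentage reads as a rate of use only if everyone in the denominator could have been recorded as a user. Here, patients without adjuvant atezolizumab stay in the denominator after collection has stopped, so they are silently counted as not taking any drug started later.

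The numerator has a separate gap. One study-wide date rule feeds two phase tables, and nothing says which table takes a peri-operative antibiotic or a steroid given for an adjuvant-phase event.

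What is at stake is the tolerability picture for adjuvant atezolizumab. The safety objective covers adjuvant as well as neoadjuvant treatment, and the protocol expects corticosteroids to be used for immune-mediated events. Table 14.1.11.3 is the planned summary of such use in the later phase.

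**Working it through.** The documents give no expected medication percentage, so there is no figure to reproduce. The check is direct arithmetic on the planning numbers.

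**Inputs**
- Safety population N: about 180 (protocol 4.1, planned enrolment, used as an approximation).
- Patients receiving adjuvant atezolizumab A: about 50 (protocol 4.1).
- Patients in the denominator with no collection after the Post-surgery Visit: 180 − 50 = 130, and 130/180 = 72%.

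**Denominator, for a drug first started in the adjuvant phase**

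Let r be the true share of adjuvant patients who use the drug. Users can be recorded only among the A patients, so the reported share is r × A/N and its ceiling, at r = 1, is A/N.

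- Ceiling: 50/180 = 27.8%. Understatement factor: 180/50 = 3.6.
- r = 20%: 10 users, 10/180 = 5.6%.
- r = 60%: 30 users, 30/180 = 16.7%.

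The value of A is uncertain, so the range is shown as an assumption:

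| A | Ceiling A/180 | Understatement 180/A | True 20% shows as |
|---|---|---|---|
| 30 | 16.7% | 6.0-fold | 3.3% |
| 50 | 27.8% | 3.6-fold | 5.6% |
| 90 | 50.0% | 2.0-fold | 10.0% |
| 120 | 66.7% | 1.5-fold | 13.3% |

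**Numerator, if no phase rule is applied**

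A drug taken only in the neoadjuvant or peri-operative period meets the SAP 6.2.5 date test. Let q be the share of all 180 patients who took it then. Assume that the remaining 1 − q of the adjuvant patients use it later at rate r. If all these records enter the later table, it shows (180q + (1 − q) × 50r)/180.

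- q = 30%, r = 0: 54/180 = 30.0%, with no adjuvant-phase use at all.
- q = 10%, r = 20%: (18 + 9)/180 = 15.0%, below the true 20%.
- q = 30%, r = 20%: (54 + 7)/180 = 33.9%, above the true 20%.

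The two faults work against each other, and which one dominates depends on the drug.

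**Comparison within the SAP**

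SAP 6.2.1 divides adjuvant-phase disposition by patients treated with adjuvant atezolizumab. SAP 6.4.1 ends the neoadjuvant adverse-event window, for patients who continue, on the day before the first adjuvant cycle. SAP 6.2.5 has neither device.

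**The case against.** A reader might infer that the two phase tables would be identical, because every on-study drug meets the single date test. The documents do not support that as the expected result. SAP 6.2.5 explicitly wants the tables separated by phase, which implies some assignment, and the adverse-event section offers a boundary that a programmer could borrow. The missing rule is under-specification.

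A reader might also infer that all adjuvant-phase percentages are understated by 72%. That does not follow either:
- The figure holds only for drugs first started in the adjuvant phase, with the numerator already confined to that phase. It cannot be combined with the identical-tables reading, under which earlier use inflates the later table.
- A chronic drug recorded as ongoing at the Post-surgery Visit can be counted for patients without adjuvant atezolizumab, because SAP 6.2.5 treats ongoing drugs as concomitant. The 28% ceiling does not apply to it.
- The figure of 50 is a planning expectation. Protocol 3.1.4 makes patients eligible on pathologic response or lack of radiographic progression, which could admit many more.

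The table shells are a separate file and might carry a different N. Nor does a population label in SAP Table 3 always fix the denominator: Table 14.1.1.2 is labelled All Enrolled Subjects, yet SAP 6.2.1 divides by adjuvant-treated patients. For medications, however, the SAP text itself names the safety population, so the label and the text agree.

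The consequence is limited. The adjuvant phase is exploratory, Table 14.1.11.3 carries no interim or primary-analysis flag, and Listing 16.2.4.3 shows every medication, so adjuvant-phase use can be recovered by hand. This bounds the importance of the point but leaves the denominator mismatch standing.

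**Conclusion.** The denominator is wrong for its purpose. As written, the table gives a share of all treated patients, and that share does not estimate use among the patients observed in the adjuvant phase. For drugs first started there, the ceiling is about 28% and the understatement 3.6-fold on the planning numbers, or 6.0-fold to 1.5-fold if 30 to 120 patients receive adjuvant atezolizumab. The lack of a phase rule is a lesser gap with an opposite effect, so no net direction can be claimed for the table as a whole. These sizes rest on 180 as the safety population and on protocol 4.4 being followed. The point is minor: the output is descriptive, and neither the primary test nor any interim rule uses it.

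**What to change.** Amend SAP 6.2.5 as follows.

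- **Table 14.1.11.3:** use as denominator the safety-population patients who received adjuvant atezolizumab. Count medications whose use overlaps the period from adjuvant Cycle 1 Day 1 to the adjuvant completion/discontinuation visit.
- **Table 14.1.11.2:** count use from first dose to the Post-surgery Visit. For patients without surgery, who have no such visit, end at the neoadjuvant treatment completion/discontinuation visit.
- **Interval between the Post-surgery Visit and adjuvant Cycle 1 Day 1:** show it separately. In Subgroup D this interval contains standard-of-care chemotherapy. Running the neoadjuvant window up to the first adjuvant cycle would report supportive drugs for that chemotherapy as neoadjuvant use.
- **Footnote to Table 14.1.11.3:** state that medications are not collected after the Post-surgery Visit in patients without adjuvant atezolizumab.

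The cost is SAP wording, date windows in two tables, one changed denominator and one small added display. No new data are needed.

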#### **6.2.6 Medical Histories**

Medical conditions will be coded to system organ classes and preferred terms using Medical Dictionary for Regulatory Activities version 19.1 or higher if available.

The number and percentage of safety population subjects who have any medical history and any medical history within the system organ class and preferred term levels will be summarized.

#### **6.2.7 Surgeries and Procedures**

Surgeries and procedures will be coded to standardized terminology.

The number and percentage of safety population subjects with any surgery or procedure, any surgery, and any procedure will be summarized.

### **6.3 Efficacy Analysis**

#### **6.3.1 Primary Efficacy Analysis**

The number of subjects with major pathologic response (n) and the major pathologic response rate ( $n/N \times 100$ ) will be summarized for the primary efficacy population (N). A one sample exact binomial test will be performed to test the null hypothesis that the major pathologic response rate is 5%, versus the alternative hypothesis is the major pathologic response rate is  $> 5\%$ . If the null hypothesis is rejected then this is evidence that the response rate exceeds 5% when atezolizumab is given before resection. The one-sided 95% confidence interval (CI) for major pathologic response rate will be reported.

### 6.3.2 Secondary Efficacy Analysis

The proportion of subjects who experienced a major pathologic response in the PD-L1 positive group (TC123IC123) and PD-L1 (TC0IC0) negative group will be compared using the Pearson's chi-square test in the primary efficacy population. If the number of subjects in one of the table cells is less than 5, then Fisher's exact test will be used instead. The lower bound of the 80% Wald CI for the difference in proportions between the two groups will be obtained. The number and the proportion of subjects with major pathologic response will be summarized by PD-L1 positive group (TC123IC123) vs. PD-L1 negative group (TC0IC0).

A similar analysis will also be performed for objective response rate: the proportion of subjects who are objective responders (Complete Response and Partial Response are considered as responders, Stable Disease, Progressive Disease and Not Evaluable are considered as non-responders) in the PD-L1 positive (TC123IC123) and negative (TC0IC0) groups will be compared using Pearson's chi-square test in the efficacy population. If the number of subjects in one of the table cells is less than 5, then Fisher's exact test will be used instead. The lower bound of the 80% Wald CI for the difference in proportions between the two groups (PD-L1 positive (TC123IC123) and negative (TC0IC0)) will be obtained. The number and proportion of subjects who are objective responders will be summarized by PD-L1 positive (TC123IC123) and negative (TC0IC0) groups.

A forest plot of major pathological responders will be produced, including the following categories:

- Sex
- Race
- Ethnicity
- ECOG performance status
- Non-metastatic lung cancer histology
- Initial diagnosis staging
- PD-L1 positive (TC123IC123) and PD-L1 negative (TC0IC0)

